The present study aims to compare the clinical outcomes of NPWT combined with HPTC skin substitute versus NPWT alone in patients with full-thickness wounds, using a randomized controlled design, to provide robust evidence for clinical decision-making in advanced wound care. Our hypothesis is that the combination therapy will result in significantly greater wound area reduction, faster closure, improved scar quality, and better patient-reported pain outcomes, without increasing adverse events.

MATERIALS AND METHODS

This was a prospective, randomized, open-label, parallel-group clinical trial conducted at the Department of Plastic, Reconstructive, and Aesthetic Surgery, Adichunchanagiri Institute of Medical Sciences (AIMS), Karnataka, India. The study compared the efficacy of Negative Pressure Wound Therapy (NPWT) combined with High Purity Type-I Collagen (HPTC) skin substitute versus NPWT alone in the management of full-thickness wounds. Patient recruitment occurred between March 2025, and July 2025. The anticipated follow-up continued until August 2025, with each participant observed for a total of seven weeks (six weeks of intervention plus one-week follow-up). The trial was registered prospectively with **ClinicalTrials.gov (ID: NCT06873867)** and approved by the Institutional Ethics Committee (**Approval No: AIMS/IEC/013/2025**). The study adhered to the principles of the Declaration of Helsinki and Good Clinical Practice guidelines. All participants provided written informed consent prior to enrollment after comprehensive explanation of study procedures, risks, and benefits. Patient confidentiality was maintained throughout the study period.

Patients aged 18-80 years with full-thickness wounds (wound depth extending through dermis into subcutaneous tissue), including traumatic, post-surgical dehiscence, burns ulcers, pressure ulcers, DFUs, or VLUs, wound size $>20 \text{ cm}^2$ and $<75 \text{ cm}^2$, with adequate vascular supply to the wound site, ability to comply with treatment protocol and follow-up visits, and provided written informed consent were eligible.

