Exclusion criteria included active infection or osteomyelitis requiring systemic antibiotics, active malignancy at wound site, immunosuppression, uncontrolled diabetes ($\text{HbA1c} > 9\%$), on systemic corticosteroids, patients on anticoagulation therapy with $\text{INR} > 3.0$ used advanced wound care products within the last 30 days, autoimmune or connective tissue disorders or allergy to bovine collagen.

Sample Size - Sample size calculation was based on the primary outcome of wound area reduction. Assuming a mean difference of 30% in wound area reduction between groups, with a standard deviation of 20%, power of 80%, and alpha of 0.05, a minimum of 47 patients per group was required. Accounting for 10% dropout rate, at 52 patients per group, with a total of 104 patients were recruited. This calculation was informed by effect sizes reported in previous HPTC RCTs in diabetic foot, venous leg and pressure ulcers, which demonstrated mean differences of 10–15% in wound healing outcomes. [6,7].

Randomization and Blinding - Participants were randomized 1:1 into two treatment groups using a computer-generated randomization sequence with block sizes of 4, 6, and 8. Patients were assigned to either: - Group A: NPWT + HPTC or Group B: NPWT alone.

Randomization was stratified by wound etiology. Allocation concealment was maintained using sequentially numbered, opaque, sealed envelopes prepared by a research assistant not involved in patient care or outcome assessment. Due to the nature of the intervention, complete blinding was not feasible; however, outcome assessors, pathologists, and data analysts were blinded to treatment allocation.

Intervention Protocol

Group A (NPWT + HPTC) - The wound was first debrided to remove necrotic tissue and ensure a viable wound bed. A sheet of High Purity Type-I Collagen skin substitute (Helicoll[®]) was applied to completely cover the wound surface. This was followed by a non-adherent porous dressing layer. NPWT was then applied using polyurethane foam at ~125 mmHg intermittent pressure (10 minutes on, 2 minutes off) for 5–7 days. The dressing was changed as per SOC thereafter, with repeat application of HPTC and NPWT as needed.

Group B (NPWT alone) - Following debridement, a non-adherent porous dressing was applied directly over the wound. NPWT was then initiated with the same parameters (polyurethane foam, ~125 mmHg, intermittent mode) and followed by SOC dressing. NPWT was reapplied if required.

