All patients received standardized wound care including sharp debridement as needed to remove non-viable tissue, infection control with topical antimicrobials when indicated, pressure redistribution and offloading as appropriate, nutritional assessment and optimization, glycemic control for diabetic patients, compression therapy for venous ulcers and pressure offloading for wounds when appropriate. Patient education on wound care was given.

Outcome Measures

The primary outcome of the study was percentage wound area reduction from week 1 through week 6 plus 1 week follow up, measured via digital photography. Measurements were performed by trained personnel blinded to treatment allocation.

Secondary outcomes included time to complete wound closure (in days) within 7 weeks, proportion of patients achieving complete closure by week 7, histological vascularity infiltration, between baseline (Day 0) and Day 5 biopsies, mean number of applications of the skin substitute required, incidence of adverse events (infection, allergic reaction, bleeding,

maceration), pain score change using a 0–10 Visual Analog Scale (VAS) from baseline to week 6, and scar quality assessed at week 7 using the Manchester Scar Scale (MSS).

Complete wound closure is defined as 100% epithelialization. Histopathological assessment included taking punch biopsies (2 mm) from the wound edge at baseline and day 5 post-intervention under local anesthesia (2% lidocaine without epinephrine). Fixation in 10% neutral buffered formalin for 24 hours, processing through graded alcohol and paraffin embedding, and serial sectioning at 4 μ m thickness was done. Samples were processed using standard histological techniques and stained with hematoxylin and eosin (H&E), Masson's trichrome, CD31 immunohistochemistry, and α -SMA immunohistochemistry. Assessment parameters included vascular infiltration (0-3 scale), neo-epithelialization (0-3 scale), fibroblast activity (0-3 scale), capillary density (vessels per mm²), inflammatory response (0-3 scale) and collagen deposition (0-3 scale) (Table 1).

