		Very high activity with extensive matrix deposition	3
Capillary density	Evaluated using CD31 staining, counted as vessels per mm^2 of tissue		
Inflammatory response	Graded semi-quantitatively (0–3 scale)	Minimal inflammatory infiltrate	0
		Mild chronic inflammation	1
		Moderate mixed inflammation	2
		Severe acute inflammation	3
Collagen deposition	Assessed using Masson's trichrome staining (0–3 scale)	Minimal collagen matrix	0
		Loose, immature collagen	1
		Moderate organized collagen	2
		Dense, mature collagen architecture	3

Table 2: Vancouver Scar Scale

Parameter	Score
Vascularity	0–3
Normal	0
Pink	1
Red	2
Purple	3
Pigmentation	0–2
Normal (matches surrounding skin)	0
Hypopigmentation	1
Hyperpigmentation	2
Pliability	0–5
Normal	0
Supple (flexible with minimal resistance)	1
Yielding (gives way to pressure)	2
Firm (resists movement)	3
Banding / rope-like tissue (may blanch on extension)	4
Contracture (permanent shortening producing deformity)	5
Height / Thickness	0–3
Flat / normal	0
< 2 mm	1
2–5 mm	2
> 5 mm	3

Parameter	Score
Total Scar Score (Higher scores indicate greater scar severity)	0-13

Data Collection and Measurement

Wound photographs were obtained using standardized digital photography with measurement grids. Standardized wound assessments were performed including digital photography, wound measurements using validated techniques, and clinical evaluations. Wound area was calculated by tracing the wound margin onto a sterile transparent film and photographing with a scale reference. Histological evaluation was performed on wound biopsies with stains as mentioned in Table 1. Pain assessments (Visual Analogue Scale) and quality of life score were completed at baseline, every week thereafter for 7 weeks.

Statistical Analysis

All data were analyzed using SPSS version 26.0 (IBM Corporation, Armonk, NY). Continuous variables were expressed as mean \pm standard deviation and compared using independent t-tests or Mann–Whitney U tests where appropriate. Categorical variables were expressed as frequencies and percentages, compared using chi-square or Fisher’s exact test. Repeated measures ANOVA was employed for longitudinal outcome analysis. Time-to-event outcomes were analyzed using Kaplan-Meier survival analysis with log-rank tests.

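### The only longitudinal method is an unadjusted repeated-measures ANOVA with no missing-data rule or analysis set; a mixed model on all observed visits is a cheap improvement, though the loss at the stated 10% dropout is small

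*Combined protocol and SAP*

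**What the plan says.** The Statistical Analysis section gives one sentence to repeated outcomes: "Repeated measures ANOVA was employed for longitudinal outcome analysis". It does not name the outcomes covered, the factors, the covariance structure or the SPSS procedure. Continuous variables in general are "compared using independent t-tests or Mann–Whitney U tests where appropriate", and time-to-event outcomes go to Kaplan-Meier and log-rank. No test is tied to any particular outcome. No analysis population, missing-data rule, covariate or sensitivity analysis appears anywhere in the document.

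Other sections bear on this:
- Sample Size: "Accounting for 10% dropout rate" is the only mention of loss. It sets the number recruited, not how leavers are analysed.
- Randomization and Blinding: "Randomization was stratified by wound etiology".
- Outcome Measures: the primary outcome, percentage wound area reduction, spans week 1 to the week-7 follow-up. Pain change is defined to week 6.
- Data Collection and Measurement: pain and quality of life are recorded at baseline and then weekly for seven weeks. No such schedule is stated for wound area.
- Materials and Methods, opening paragraph: "Patient recruitment occurred between March 2025, and July 2025" and "The anticipated follow-up continued until August 2025, with each participant observed for a total of seven weeks".

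**The concern.** Classical repeated-measures ANOVA works on one row per patient and uses only rows with every modelled visit filled. A patient who leaves at week 5, or who misses only week 3, then contributes nothing. The comparison would describe complete attenders rather than the randomised groups. It would lose some precision, and it would be biased if patients who heal poorly are more, or less, likely to have gaps. The bias could go in either direction if this pattern differs by arm.

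Two further weaknesses do not depend on deletion. An analysis that ignores a prognostic stratification factor or the baseline value gives up precision. And because no test is assigned to the primary outcome, a reader cannot tell which patients, which week and which comparison carry the main result.

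**Working it through.** **Inputs.** From Sample Size: 52 per arm, SD 20 points, difference 30 points, dropout 10%. Assumed: seven weekly post-baseline visits for wound area; a leaver's last attended visit is equally likely to be any of weeks 0 to 6; any sporadic misses are independent at rate m per visit.

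**The plan's own figures.** 47 × 1.10 = 51.7, which rounds to the stated 52; 47 / 0.90 = 52.2 would give 53. The 47 itself does not follow from its inputs: 2 × (1.960 + 0.842)² × 20² / 30² = 6.98, so 7 per arm. That is a separate matter and is not used below.

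**Complete records per arm** = 52 × 0.90 × (1 − m)^7.

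**Complete-record standard error at week 7** = 20 × √(2 / complete records). At m = 0: 20 × √(2/46.8) = 4.13.

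**Mixed-model standard error at week 7.** Sum, over all missingness patterns, the probability of the pattern times the inverse covariance of the visits it observes. Multiply by 52, invert, take the week-7 diagonal element, double it and take the square root. This uses free weekly means per arm, known covariance and no covariates. Under AR(1) correlation 0.8 and m = 0 the result is 4.08. The ranges below cover AR(1) 0.5, 0.8 and 0.9 and compound symmetry 0.5 and 0.8.

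| Missed per visit | Complete per arm | Complete-record v mixed-model SE, AR(1) 0.8 | Excess (range) | Observed visits discarded |
|---|---|---|---|---|
| 0 | 46.8 | 4.13 v 4.08 | 1.3% (0.3–3.3%) | 4.5% |
| 2% (illustrative) | 40.6 | 4.44 v 4.10 | 8.3% (6.8–10.6%) | 15.4% |
| 5% (illustrative) | 32.7 | 4.95 v 4.12 | 20.0% (17.6–22.8%) | 29.8% |

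Only the first row rests on a loss rate in the document. Its discarded share can be checked by hand. Leavers attend 3 visits on average, so observed visits per patient are 0.9 × 7 + 0.1 × 3 = 6.6, and the discarded share is 0.3 / 6.6 = 4.5%.

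**A week-7 t-test instead.** It uses everyone seen at week 7. Under AR(1) 0.8 its standard error exceeds the mixed model's by 1.3%, 1.9% and 2.8% in the three rows. At m = 0 it uses the same 46.8 patients per arm as the complete-record ANOVA.

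**Power.** At 30 points, 30 / 4.13 = 7.3 standard errors, so power is about 100%; it stays there in every row.

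**Bias, illustration only.** In a simulation with SD 20, AR(1) 0.7, about 9–10% dropout and poor healers leaving more often, the complete-record week-7 difference averaged 29.0 against a true 30, and 11.0 against a true 11.56. A likelihood estimate from all observed weeks gave 30.0 and 11.4.

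**Missing week 7 in the proposed analysis set.** One seventh of leavers have no post-baseline value: 0.10 / 7 = 1.43% of patients, or 52 × 0.0143 = 0.74 per arm. Among those analysed, (10 − 1.43) / (100 − 1.43) = 8.7% lack week 7.

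**Dates.** 31 August minus 49 days is 13 July; enrolment on 31 July reaches week 7 on 18 September. From 1 March to 31 July is 153 days, of which 18 (14–31 July) are too late. With uniform accrual 18/153 = 11.8% of patients are affected, about 12 of 104. With accrual rising linearly from zero, 1 − (135/153)² = 22%, about 23 of 104. If enrolment had stopped by 13 July, none are.

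**The case against.** The strongest reply is that deletion of incomplete patients is not documented. The section names the software but no procedure, so a reader might infer listwise deletion from the name of the method; the document does not say this. That stands, and the point is therefore conditional.

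Second, at the only stated loss rate the cost is negligible, and the sample size already allowed for it: 46.8 complete patients against 47 required. A week-7 t-test, which the same section permits, avoids most of the loss even with sporadic misses. That stands too. The 8.3% and 20.0% figures rest on assumed rates and are not evidence about this trial.

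Third, weekly wound-area visits are an assumption; the primary outcome may be a single change. For pain, defined to week 6, six visits would leave 46.8 × 0.98^6 = 41.5 or 46.8 × 0.95^6 = 34.4 complete per arm at 2% or 5% missed, slightly more than in the table.

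Fourth, a reader might infer from the dates that late enrollees lack week 7. The text says every participant was observed for seven weeks and calls the end of follow-up anticipated. Follow-up may have run past August, or enrolment may in effect have stopped by mid-July. The dates call for reconciliation and do not show missing data.

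What the reply does not remove is that the only longitudinal method is unadjusted for baseline and etiology, and that no rule says who is analysed or how gaps are handled.

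**Conclusion.** The point holds as a worthwhile improvement, not as a demonstrated flaw in the result. The plan's longitudinal method is weaker than one available in the same software, and the analysed population is undefined.

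If the ANOVA is run on complete records, with weekly wound-area visits and uniform dropout timing, the stated 10% dropout costs about 1.3% in the week-7 standard error (0.3% to 3.3%) and 4.5% of observed visits. Power at the planned difference is untouched. Kaplan-Meier is not affected.

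The document does not support the stronger inference that the primary result is biased or materially underpowered by this choice. It does not say that the ANOVA is the primary test, it gives no missed-visit rate, and bias requires missingness related to healing. The simulated shift of about 0.5 to 1 point depends on its own assumptions; the actual size cannot be derived from the document. The gain from adjusting for baseline and etiology cannot be quantified either, because no correlation with outcome is given.

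**What to change.** For wound area reduction, pain and quality of life, replace the ANOVA with a linear mixed model (SPSS MIXED, REML):
- Data: all observed visits of all randomised patients with at least one post-baseline value.
- Terms: treatment, week, treatment-by-week, etiology and the baseline value (baseline wound area for wound area reduction).
- Contrast: week 7, or week 6 for pain. Name the week-7 contrast as the primary comparison for wound area reduction.
- Closed wounds: the plan says "Complete wound closure is defined as 100% epithelialization" but not how later visits are scored. State this, including how a missed visit after closure is handled.
- Not-at-random check: lower the missing combination-arm week-7 values in steps. With about 8.7% of that arm missing, each 10 points lowers the contrast by 0.087 × 10 = about 0.87 points.
- Reporting: numbers missing by arm and visit, and numbers with no post-baseline value.

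Separately, reconcile the recruitment and follow-up dates and give the date of the last week-7 visit.

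**Cost.** Text and another procedure in the same software; no new data. A covariance structure with a fallback must be specified (unstructured over seven visits has 7 × 8 / 2 = 28 parameters). The model assumes data missing at random and still leaves out about 0.7 patients per arm with no post-baseline value. Reduction is capped at 100%, so late-week residuals may be skewed. The document is dated November 2025 and written in the past tense. If the ANOVA has already been run, report both results and label the mixed model post hoc.
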